1.3 Preclinical Data

In vitro testing has shown that the solubility of hydroxyapatite is enhanced when mixed with a poly-lactic acid oligomer (13). Human studies have shown that reabsorption rates of hydroxyapatite was approximately 20% annually with no adverse reaction seen in the surrounding bone (13). A 6 week porcine bone defect model showed, when compared to bone wax, BoneSeal® had an equally effective hemostatic action. Histomorphometric data showed significantly greater new bone growth as compared to bone wax (14). Furthermore, fibrous tissue was significantly less as compared to bone wax (14).

1.4 Clinical Data to Date

Currently there is no relevant, specific clinical data regarding BoneSeal® at this time. BoneSeal®, is FDA cleared based on the determination that the device is substantially equivalent to currently cleared marketed predicate devices.

1.5 Dose Rationale and Risk/Benefits

Dosage regimen is as follows: 1 to 2 units (2.5 or 3.5 grams) per surgery as determined by the surgeon. This is based on the common amount of the comparable product used and the amount needed to obtain immediate hemostasis during surgery.

2 Study Objectives

A prospective randomized open-label study that will evaluate the effectiveness of the pliable and absorbable bone hemostats (BoneSeal®) composed of synthetic materials and hydroxyapatite on the reduction of bleeding from the sternal bone marrow in patients undergoing Coronary Artery Bypass Grafting, with or without valve replacement or repair. This product will be compared to the similar, currently used product, Ostene®. Bleeding will be evaluated qualitatively by the surgeon as well as quantitatively by comparing pre- and post-operative hemoglobin levels, intra-operative and post-operative blood product usage, and post-operative chest tube output. A 30 day follow-up will be conducted to evaluate the patient's tolerance of the product, possible complications, or infection. Additionally, surgeons will be asked to comment on the ease of use of the product.

3 Study Design

3.1 General Design

- Design: Prospective randomized trial
- Qualitative hemostatic action during application and quantitative evaluation of post-operative hemoglobin, intra- and post-operative blood product usage, and post-operative chest-tube output.
- Duration of subject participation: 30 days post procedure

3.2 Primary Study Endpoints

- 1) Qualitative determination of bleeding and hemostatic action during application graded by the surgeon using the mild, moderate, and severe for bleeding and complete, moderate, minimal, and failure for hemostatic action.

CONFIDENTIAL

This material is the property of the Loma Linda University Medical Center. Do not disclose or use except as authorized in writing by the study sponsor

- 2) Occurrence of re-bleeding during the operation will be noted. Reapplication of product will not occur.
- 3) Postoperative hemoglobin as compared to baseline preoperative readings.
- 4) Post-operative chest tube output.
- 5) Intra-operative and post-operative blood product transfusion quantities.
- 6) Sternal wound infection or other complications within 30 days post procedure.

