12.1	FUNDING SOURCE	19
12.2	CONFLICT OF INTEREST	19
12.3	DISCLOSURE	20
12.4	SUBJECT STIPENDS OR PAYMENTS.....	20
13	PUBLICATION PLAN	20
14	REFERENCES.....	20
15	ATTACHMENTS	21

CONFIDENTIAL

This material is the property of the Loma Linda University Medical Center. Do not disclose or use except as authorized in writing by the study sponsor

List of Abbreviations

CRF	Case Report Form
FDA	Food and Device Administration
GCP	Good Clinical Practice
IRB	Institutional Review Board
HA	Hydroxyapatite
PLA	Poly-lactic acid
PEG	Polyethylene glycol
CABG	Coronary Artery Bypass Grafting
OR	Operating Room

CONFIDENTIAL

This material is the property of the Loma Linda University Medical Center. Do not disclose or use except as authorized in writing by the study sponsor

Study Summary

Title	Effectiveness of BoneSeal® on sternal bone hemostats in patients undergoing cardiothoracic surgery
Short Title	Effectiveness of BoneSeal®
Protocol Number	Not yet assigned
Methodology	Prospective, randomized, open-label, study design
Study Duration	Estimated duration for the main protocol (start of screening November 2016) to (last subject processed and finishing the study November 2017)
Study Center(s)	Single-center
Objectives	To evaluate the effectiveness of BoneSeal® on bone hemostats in patients undergoing cardiothoracic surgery.
Number of Subjects	60
Diagnosis and Main Inclusion Criteria	Adult patients over 18 years undergoing coronary artery bypass grafting with or without valve replacement or repair ultimately requiring a sternotomy.
Study Product, Dose, Route, Regimen	BoneSeal® Bone Wax Hemostats Dosage regimen is as follows: 1 to 2 units (2.5 or 3.5 grams) per surgery as determined by the surgeon.
Reference therapy	Ostene®
Statistical Methodology	Statistical methods for evaluating postoperative bleeding and need for blood transfusions will include a Fisher's exact test (2 groups, 2 outcomes).

CONFIDENTIAL

This material is the property of the Loma Linda University Medical Center. Do not disclose or use except as authorized in writing by the study sponsor

1 Introduction

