3.3 Secondary Study Endpoints

- 1) Ease of use of BoneSeal® compared to Ostene® – graded by primary surgeon using a Likert-scale (ranging from 1 [very easy] to 5 [very difficult]).

4 Subject Selection and Withdrawal

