5.5.4 Return or Destruction of Study Device

At the completion of the study, there will be a final reconciliation of device shipped, device consumed, and device remaining. This reconciliation will be logged on the device reconciliation form, signed and dated. Any discrepancies noted will be investigated, resolved, and documented prior to return or destruction of unused study device. Device destroyed on site will be documented in the study files.

6 Study Procedures

6.1 Study Data Point 1

Hemostasis during surgery will be determined by surgeon's qualitative evaluation. Notation of re-bleed will be made. Re-application of product will not occur.

6.2 Study Data Point 2

Postoperative bleeding will be evaluated by documentation surgical site drainage and the use of blood products.

6.3 Study Data Point 3

30 day post-op follow-up to all for sufficient time to heal and evaluate for possible post-operative infection or complications. This evaluation can be conducted either in person or by phone.

CONFIDENTIAL

This material is the property of the Loma Linda University Medical Center. Do not disclose or use except as authorized in writing by the study sponsor

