12.3 Disclosure

Let it be disclosed that [name] served as a medical expert in the production of the study device. He did not receive payment for his expertise, nor is he on any patents related to the product.

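### Open-label surgeon grades serve as endpoints, and nothing visible keeps a person with a disclosed role in producing BoneSeal from giving them

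*Combined protocol and SAP*

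**What the plan says.** The Study Summary describes the trial as "Prospective, randomized, open-label, study design". Under 5.3 the investigator confirms the opened envelope. Under 5.5.3 the study investigators are told the allocation, and one of them fetches the product before surgery.

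Section 3.2 lists six primary endpoints without ranking them:

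- Item 1 is "Qualitative determination of bleeding and hemostatic action during application graded by the surgeon", with three levels for bleeding and four for hemostatic action. Section 6.1 repeats the point: "Hemostasis during surgery will be determined by surgeon's qualitative evaluation".
- Item 2 reads "Occurrence of re-bleeding during the operation will be noted". Neither 3.2 nor 6.1 says who notes it or by what criterion.
- Items 3 and 4 are "Postoperative hemoglobin as compared to baseline preoperative readings" and "Post-operative chest tube output".
- Items 5 and 6 are transfusion quantities, and wound infection or other complications within 30 days.

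The only secondary endpoint (3.3) is ease of use, "graded by primary surgeon using a Likert-scale" from 1 to 5.

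Section 12.3 discloses that a person, whose name is masked in the public copy, "served as a medical expert in the production of the study device". It adds that the person was not paid and holds no patent on the product. Section 12.2 sends investigators' conflicts of interest to a committee for review and a management plan, and binds the institution's investigators to the University policy.

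**The concern.** The operating surgeon handles the product and cannot easily be blinded to it. The main control left for a subjective grade is therefore the choice of grader. Someone who contributed to one arm's product has a foreseeable direction of preference. Randomization balances patients between arms, but it does not balance a grader's preference for one product, and that preference does not average out with more cases.

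The six primary items have no hierarchy, so a favourable surgeon grade could be reported alone as a primary finding. The trial has one center and 60 subjects, so one surgeon could supply a sizeable share of the grades.

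**Working it through.** **Step 1: which endpoints depend on a surgeon's judgement**

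| Endpoint | Source | Surgeon grade? |
|---|---|---|
| Bleeding and hemostatic action (primary 1) | 3.2, 6.1 | Yes |
| Re-bleeding (primary 2) | 3.2, 6.1 | Assessor not named |
| Hemoglobin (primary 3) | 3.2 | No |
| Chest tube output (primary 4) | 3.2 | No |
| Transfusion quantities (primary 5) | 3.2 | No |
| 30-day infection or complications (primary 6) | 3.2 | No |
| Ease of use (secondary) | 3.3 | Yes |

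The exposed endpoints are primary 1 and the secondary, with primary 2 possible. Four of the six primary items are not surgeon grades.

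**Step 2: is the disclosed person kept from grading?**

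Sections 3.2, 3.3, 5.3, 5.5.3, 6.1, 6.4 and 7.2 describe no blinded or independent assessor, second rater, grade definitions or adjudication. Section 12.3 states a link to the device but no trial role. The examples in 12.2 are patents, royalties and financial gain. The list is left open, but 12.3 says this person has neither payment nor patents, and 12.2 does not say who may grade outcomes. No visible text settles the question.

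**Step 3: how much could it matter? (illustration only)**

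The plan has no figure to reproduce. Section 7.1 says that 60 was not derived statistically and raises alpha to an unstated level. Section 7.2 gives only descriptive statistics for hemostasis scores and ease of use.

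Assumptions, none from the documents except the total of 60: 30 per arm; no true difference; a two-sided t-test; the person favours BoneSeal by 0.5 SD in a fraction *f* of cases, spread evenly over the arms; the SD is otherwise unchanged.

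- Average shift: d = f × 0.5 SD.
- Noncentrality: d × √(30/2) = 3.873 × d, with 30 + 30 − 2 = 58 degrees of freedom.
- Two-sided critical values: 2.002 at 5% and 1.672 at 10%. The 10% level is shown because the raised alpha is not given.

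| Fraction f | d (SD) | Noncentrality | Significant at 5% | Significant at 10% |
|---|---|---|---|---|
| 1/4 | 0.125 | 0.484 | 7.6% | 13.9% |
| 1/2 | 0.25 | 0.968 | 15.9% | 25.0% |
| 1 | 0.5 | 1.936 | 47.8% | 60.6% |

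A second model treats hemostatic action as complete or not, with Fisher's exact test and 30 per arm. Suppose 50% are truly complete in both arms.

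- No grading bias: rejection probability 2.7% at alpha 0.05 and 5.2% at 0.10.
- A quarter of the non-complete BoneSeal cases graded up (50% + 0.25 × 50% = 62.5%): 10.7% and 16.8%.
- Half graded up (50% + 0.5 × 50% = 75%): 41% and 53%.
- If 70% are truly complete: 5.9% and 10.7% with a quarter graded up (77.5%), and 19% and 28% with half graded up (85%).

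Both models point the same way, and the size depends on inputs that the documents do not supply.

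**The case against.** The strongest objection is that the person's role in the trial is not visible. The name is masked and the title and signature pages were removed, so the complete document may show at once whether this is a study surgeon. Without that link, what remains is ordinary surgeon grading in an open-label trial. This stands, and it makes the point conditional. It does not remove it, because no visible section on endpoints or procedures says who may grade.

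Second, 12.2 is not limited to its examples, and the University policy cannot be seen, so the link may already be managed. That is possible. But review by a committee does not in itself take a person out of grading, and 12.2 does not require it to.

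Third, a reader might infer that the trial's result reflects the developer's own judgement. The documents do not support this. They describe an unpaid expert without patents, do not show that this person operates or grades, and list four primary items that are not surgeon grades. For re-bleeding, naming the surgeon as assessor is itself an inference.

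Fourth, a reader might take 16% or 48% as this trial's false-positive rate. It is not. The plan names no test for these scores, endpoint 1 is ordinal, alpha is unstated, and the 0.5 SD preference and the shares of cases are assumed. Only the direction carries over: a biased descriptive contrast misleads too.

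**Conclusion.** The point holds conditionally and with limited scope. Primary endpoint 1 and ease of use are open-label grades by the operating surgeon, re-bleeding has no named assessor, and nothing visible keeps the person disclosed in 12.3 from giving these assessments. If that person is a study surgeon, these endpoints can be biased toward BoneSeal. Hemoglobin, chest tube output, transfusion quantities and 30-day complications are not surgeon grades and fall outside the point.

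The size cannot be derived from the plan. Under the stated assumptions, the chance of a spurious significant difference at the 5% level runs from about 8% (a quarter of cases) through 16% (half) to 48% (all). These figures show only that a moderate preference could matter with 60 subjects.

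**What to change.** 1. Record on the case report form which surgeon graded each case.
2. In 7.2, pre-specify that endpoint 1, re-bleeding and ease of use are also reported without cases graded by anyone with a role in producing either device. State that no BoneSeal advantage on these endpoints will be claimed unless it persists in that analysis or is supported by the measured endpoints (chest tube output, hemoglobin, transfusion).
3. In 3.2 and 6.1, state that where another surgeon is already taking part in the case, that surgeon records the endpoint 1 and re-bleed items in place of the disclosed person. The documents do not say that a second surgeon is always present, so this applies only where one is. No extra assessor is required. The substitute may also know the arm, so this removes the specific interest and not all open-label bias.
4. If the person has no grading role, say so in 12.3. Steps 2 and 3 then need not be invoked for that person.

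The cost is one form field and a few sentences. The downside is a smaller sensitivity analysis: if the person graded a quarter of the 60 cases, 45 remain; if half, 30. Section 5.3 describes no stratification by surgeon, so the arms in that subset may be unequal. If the person operates on nearly all cases, the analysis is uninformative and the conclusion should rest on the measured endpoints. Section 2 speaks of surgeons in the plural, which suggests that other surgeons' cases will remain, but it does not guarantee this.

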3.3 Secondary Study Endpoints

- 1) Ease of use of BoneSeal® compared to Ostene® – graded by primary surgeon using a Likert-scale (ranging from 1 [very easy] to 5 [very difficult]).

4 Subject Selection and Withdrawal

4.2 Exclusion Criteria

Exclusion criteria include patients with the following:

- 1) An immune system disorder
- 2) Known hypersensitivity to components in BoneSeal® or Ostene®
- 3) Patients undergoing emergency surgery
- 4) Patients undergoing aortic dissection
- 5) No consent given

4.3 Subject Recruitment and Screening

Subjects will be recruited for the study from the International Heart Institute's clinic, referring physicians. The principal investigator and study physicians will screen the patients based on their ability to meet inclusion criteria and a medical chart review.

4.4 Early Withdrawal of Subjects

4.4.1 When and How to Withdraw Subjects

Patients will be withdrawn from the study prior to their expected completion if they meet one of the exclusion item criteria's after their primary surgery, if the investigator believes they should be withdrawn due to safety reasons or failure of subjects to adhere to protocol requirements (such as a need for emergency surgery).

CONFIDENTIAL

This material is the property of the Loma Linda University Medical Center. Do not disclose or use except as authorized in writing by the study sponsor

4.4.2 Data Collection and Follow-up for Withdrawn Subjects

If a subject withdraws consents to participate in the study, attempts will be made to obtain permission to record survival data. Subjects considered lost to follow-up require at least 3 phone calls to the subject.

5 Study Device

5.1 Description

BoneSeal® is an absorbable synthetic bone hemostats that also contains of PLA, PEG and hydroxyapatite which supports bone re-growth. The product is packaged as 5 single use, sterile units (2.5-3.5 gram ingot) per carton. One sterile unit contains one ingot. Sterilization is by gamma irradiation. BoneSeal® has FDA approval (K142348).

5.2 Treatment Regimen

BoneSeal® is applied to the cut surfaces of the sternum under the direction of a licensed healthcare provider. The material forms a mechanical barrier that occludes the vascular openings on the spongy bone of the sternum. It is left on the site and ultimately reabsorbed by the body with no expected adverse effects.

5.3 Method for Assigning Subjects to Treatment Groups

Subjects will be randomized on the day of surgery. A number will be assigned to each package – study device and control. This number will be printed on a page and a page sealed that is then sealed in an envelope. On the day of surgery, an envelope will be pulled and opened by the OR Coordinator and confirmed by the investigator. The corresponding number will be selected from the labeled packages. The printed number will be labeled with the subject's information filed as a source document. The number and corresponding assignment (study device or control) will be noted in the patient's record.

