5.4 Packaging and Administration of Study Device

The device comes ready packaged and sterile for use. Each unit is a 2.5-3.5 gram ingot that can be molded as needed by the surgeon and applied to the cut site of the sternum. The control comes similarly packaged. Each dosage of either the study device or the control should be individually separated and numbered. Individual envelopes with printouts of the corresponding numbers will be used for randomization.

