5.5.2 Storage

The device and the control will be stored in a locked file cabinet with the OR Coordinator.

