5.5.3 Dispensing of Study Device

Once randomization has occurred the study investigators will be notified of the study patient's treatment allocation and the printout kept with the study patient's source documents. The study patient's charts will be labeled in order for them to easily be recognized as a study patient. The morning of the planned surgery, the Nurse Manager in the operating room will be notified that the patient is a study patient and that they will receive BoneSeal or Ostene during the surgery. The study investigator will obtain the product prior to the start of surgery. The study device will be kept with the OR Coordinator in a locked file cabinet in order for the study device to remain separate and in a temperature controlled environment. Regular study device reconciliation will be performed to document treatment assigned, treatment consumed, and treatment remaining. This reconciliation will be logged on the device reconciliation form, and signed and dated by the Principal Investigator.

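### Section 5.3 assigns treatment by an envelope draw with no stated sequence, opening order, opacity or opening log, so allocation concealment is not assured

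*Combined protocol and SAP*

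**What the plan says.** Sections 5.3 and 5.4 hold the whole allocation method.

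- **Numbering.** "A number will be assigned to each package – study device and control" (5.3). The number belongs to a package; it is not described as a subject number or a place in a sequence.
- **Envelopes.** "Individual envelopes with printouts of the corresponding numbers will be used for randomization" (5.4). Section 5.3 says they are sealed.
- **Drawing.** "On the day of surgery, an envelope will be pulled and opened by the OR Coordinator", with confirmation by the investigator (5.3).
- **Custody.** "The device and the control will be stored in a locked file cabinet with the OR Coordinator" (5.5.2). The protocol does not say who keeps the envelopes.
- **Collection.** "The study investigator will obtain the product prior to the start of surgery" (5.5.3).
- **Records.** The printed number is labelled for the subject and filed, and number and arm go into the patient's record (5.3). Product assigned, used and left over is reconciled on a form signed by the Principal Investigator (5.5.3), with a final reconciliation at study end (5.5.4).
- **Supply unit.** "Each dosage of either the study device or the control should be individually separated and numbered" (5.4), while the amount is "1 to 2 units (2.5 or 3.5 grams) per surgery as determined by the surgeon" (1.5).

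No section states how the sequence is generated, the allocation ratio, any blocking, the order in which envelopes are used, their opacity, an opening log, or an independent custodian.

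**The concern.** Concealment means that nobody can know or change the next assignment once a particular patient is in view. Sealed envelopes achieve this only if their order is fixed in advance and each is tied to a subject before it is opened. Section 5.3 requires neither. The only subject identification it describes is put on the printed number, which is inside the envelope.

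The setting makes this matter. The trial is single-centre and open-label (Study Summary), and two of the items that the surgeon grades, bleeding and hemostatic action, are primary endpoints (3.2). If assignment came to depend on perceived bleeding risk, the arms would differ at baseline. That would also affect the measured endpoints: hemoglobin, chest tube output and transfusion. The ANCOVA in 7.1 names no covariates, so it cannot be relied on to repair such a difference. No misconduct is suggested; the procedure as written does not prevent it.

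**Working it through.** **1. Would the existing records show a departure?** The protocol gives no figure to reproduce, so the check begins with the text. Two departures are compared: using a product that does not match the drawn number (swap), and opening an envelope, rejecting it and taking another (redraw).

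| Safeguard | What it captures | Swap | Redraw |
|---|---|---|---|
| Investigator's confirmation (5.3) | Not stated what is confirmed | Likely shown | Not reliably; investigators also screen patients (4.3) and collect the product (5.5.3) |
| Filed printed number (5.3) | Number finally used | Shown | Not shown; labelled after opening |
| Chart entry (5.3) | Number and arm finally used | Shown | Not shown |
| Reconciliation (5.5.3, 5.5.4) | Product assigned, consumed, remaining | Shown | Not shown; counts still balance |

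**2. What one redraw does.** Assume 60 envelopes, 30 per arm. The 60 is from the Study Summary; the 1:1 ratio is my assumption. For the first patient:

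- no redraw: P(wanted arm) = 30/60 = 50.0%
- one redraw with the rejected envelope set aside: 1 − (30/60 × 29/59) = 75.4%

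**3. Illustrative effect on type I error.** Further assumptions: half the patients are high-risk; control is wanted for high-risk patients and BoneSeal for the rest; when the opened envelope shows the unwanted arm, it is redrawn once with probability q and the rejected envelope goes back. The true effect is zero, the outcome differs between risk groups by 0.5 or 1.0 SD, and a two-sample t-test is used (4000 simulations per setting). Expected redraws are about 60 × 0.5 × q = 30q. The protocol says alpha is increased (7.1) but not to what, so two levels are shown.

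| q | Redraws | Excess proportion of high-risk patients in control | Type I error at nominal 5% (gap 0.5 / 1.0 SD) | At nominal 10% (gap 0.5 / 1.0 SD) |
|---|---|---|---|---|
| 0 | 0 | 0.00 | 5.1% / 4.7% | 10.3% / 9.4% |
| 0.10 | 3 | 0.05 | 5.4% / 5.3% | 10.9% / 11.3% |
| 0.25 | 7.5 | 0.12 | 5.9% / 6.8% | 11.2% / 13.1% |
| 0.50 | 15 | 0.25 | 7.3% / 13.1% | 13.2% / 21.1% |
| 1 | 30 | 0.50 | 15.1% / 41.2% | 24.3% / 54.2% |

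The simulation error near 5% is √(0.05 × 0.95 / 4000) = 0.34 percentage points, so q = 0.10 cannot be told apart from nominal. Bias is the excess proportion times the gap: at q = 0.50, 0.25 × 0.5 = 0.12 SD to 0.25 × 1.0 = 0.25 SD. Every run ended 30/30, so a count of product used would have shown nothing.

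**4. Which list to use in the fix.** Suppose someone tracks the arm counts and always guesses the arm that is behind. For m + m assignments the expected correct guesses are m + 0.5 × 2^(2m)/C(2m, m) − 0.5.

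- One 30+30 list: 30 + 4.87 − 0.5 = 34.4 of 60
- Blocks of 4: 2 + 0.5 × 16/6 − 0.5 = 2.83 per block; 15 × 2.83 = 42.5 of 60
- Blocks of 6: 3 + 0.5 × 64/20 − 0.5 = 4.1 per block; 10 × 4.1 = 41.0 of 60
- Sizes 4 and 6 mixed at random: 41.4 of 60

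Mixing sizes hardly helps, because the guesser needs only running counts, which are visible in an open-label single-site trial.

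**The case against.** Much of the case on the other side stands.

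- **The protocol never says the envelopes are unordered.** A reader might infer a loose pool from the word used for drawing. The text is silent on order and on who holds the envelopes. What stands is that no order is required.
- **There are records and a second person.** A reader might infer that assignment could be altered without leaving any trace. That goes too far: a swap against the drawn number would show in the filed number, the chart or the reconciliation, and a broken seal is itself evidence. But nobody is asked to keep or inspect envelopes, and the confirming investigator is not independent.
- **Roles are partly separated.** Investigators screen, and the OR Coordinator has no stated screening or grading role. This lowers the risk. It does not remove it, because the opener stores both products and the investigator takes part on the day.
- **The second-unit worry is ambiguous.** A reader might infer that a second unit would have to come from a package tied to an unopened envelope. That follows only if a dosage in 5.4 means one unit. Sections 1.5 and 5.4 can equally be read as making the dosage the whole supply for one surgery. The wording needs reconciling; no error is shown.
- **Predictability and imbalance are not evidence of steering.** The 34.4 correct guesses belong to any fixed 30+30 list, however well concealed. The 15.5% chance of a split of 36:24 or worse is ordinary simple randomisation.

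**Conclusion.** The point holds as a weakness of procedure. Followed exactly, 5.3 does not prevent an envelope from being opened, rejected and replaced, and the listed records would not reliably reveal it. This is more than missing detail, since a better and cheap method exists.

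The documents do not show that steering would occur, or how large its effect would be. The figures above rest wholly on assumed redraw frequency, direction, risk gap and a 30/30 pool. Within those assumptions, occasional redraws change little and systematic ones inflate type I error substantially. It would be wrong to quote any of them as the bias of this trial. The change is best classed as a cheap improvement.

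**What to change.** **Section 5.3.** Replace the draw with sequentially numbered, opaque, sealed envelopes prepared from one computer-generated 1:1 list, for example a single random permutation of 30+30. State the ratio. Have the list prepared and held by existing study staff who do not enrol, operate or store product. Write subject ID, date and time on the next envelope before opening it, open strictly in order, and keep every envelope together with a log of openings. Avoid small blocks, for the reason shown in the working.

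**Section 5.4.** Reconcile the numbered dosage with the amount in 1.5 by stating that one package number covers one subject's whole supply. This concerns numbering only and leaves the amount used untouched.

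**Cost.** About an hour of preparation and a paragraph across the two sections, with no extra staff. Some predictability remains near the end of a 30+30 list. Simple randomisation would remove it, at the price of the 15.5% chance of a 36:24 or worse split.
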